4.7.5. Removal of Subjects from Study Treatment

A subject may discontinue study treatment for any of the following reasons:

1. Occurrence of any medical condition or circumstance that, in the opinion of the Investigator, exposes the subject to substantial risk and/or does not allow the subject to adhere to the requirements for investigational product as per the Protocol.
2. Adverse Events as described in [Section 5.9](#) the Investigator must follow the subject until the AE resolves or satisfactorily stabilizes.
3. Treatment must be discontinued immediately in the event of a female subject's pregnancy.
4. Subject's decision to discontinue treatment with study drug.
5. C-SSRS ([Section 5.1.10](#)) indicative of suicidal ideation (score > 0).
6. PHQ-8 ([Section 5.1.7](#)) or modified PHQ-A ([Section 5.1.8](#)) score ≥ 15 if determined by Investigator in consultation with mental health professional.
7. CDI-2 ([Section 5.1.9](#)) raw total score of ≥ 32 if determined by Investigator in consultation with mental health professional.

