4.7.6. Removal of Subjects from the Study

A subject may be removed from study participation for any of the following reasons:

1. Subject death.
2. Subject's decision to withdraw from study.
3. Subject is lost to follow-up. A subject will be considered lost to follow-up after three phone and three email attempts and documentation of a certified letter sent to the subject's address.

4. Requirement for use of prohibited concomitant medication after consultation with the Sponsor and Medical Monitor.
5. Subject's repeated failure to comply with protocol requirements or study related procedures.
6. The subject interrupts trial study drug application for more than 50% of scheduled doses.
7. Termination of the study by the Sponsor, FDA, or other regulatory authorities.

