5.5 Derived Variables

All questionnaire scores will be derived by Biostatistics in the ADaM datasets using the formulas defined below, even if calculated scores are present in the EDC database. All pre-calculated scores will be ignored for analysis.

- With the following exception, vIGA-AD Score of Clear (0) or Almost Clear (1) = vIGA-AD of ‘Clear’ (0) or ‘Almost Clear’ (1). The exception is that for subjects who discontinued early from study due to an AE or lack of efficacy, the subject will be considered as not having a vIGA-AD score of Clear (0) or Almost Clear (1) for all pre-specified analysis visits (refer to Section 5.4) for which the subject’s day of last dose falls within or is before the start of the analysis visit window.
- With the following exception, vIGA-AD Success = vIGA-AD of ‘Clear’ (0) or ‘Almost Clear’ (1) plus at least a 2-grade improvement from baseline. The exception is that for subjects who discontinued early from study due to an AE or lack of efficacy, the subject will be considered as not having a vIGA-AD success for all pre-specified analysis visits (refer to Section 5.4) for which the subject’s day of last dose falls within or is before the start of the analysis visit window. vIGA-AD Success will be derived for both the Primary and OLE baselines (refer to Section 5.2)
- Date of last contact = the latest of last study visit date, last dose date, end-of-study date and end-of-treatment date.
- Post-OLE Week 4 study duration (days): The duration can be represented as End Date – Start Date +1. The start date of the Post-OLE Week 4 interval will be the date of the OLE Week 4 visit or OLE Day 29 if the subject missed the OLE Week 4 visit. The end date will be the date of last contact. This endpoint will be calculated only for subjects who enter the post-OLE Week 4 study period.
- Duration (days) of the first BIW dosing will be calculated from the first BIW dosing to the start of the succeeding QD dosing interval. Subject’s last contact date will be used to censor

 Innovaderm Research	STATISTICAL ANALYSIS PLAN, Final Version 1.0
Protocol Number: ARQ-151-313	Sponsor: Arcutis Biotherapeutics, Inc.

this endpoint (time-to-event analysis) or as the end date of this duration (analyzed as a continuous endpoint) for subjects who do not revert to a QD dosing regimen after the first BIW dosing. This endpoint will be calculated only for subjects who enter the post-OLE Week 4 study period with at least one BIW dosing interval.

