6.2.1 Multiple Imputation

For the vIGA-AD secondary efficacy endpoints (refer to Section 12.2), vIGA-AD non-imputed values collected during the parent studies and this study (including the last available data of subjects who prematurely withdraws from this study) will be appended together after having been assigned to pre-specified analysis visit using the analysis windows defined in their respective study (parent study SAPs or this SAP Section 5.4, as applicable). Doing so, each subject will have between 4 (subjects who enrolled in OLE and discontinued early before the first application of

 Innovaderm Research	STATISTICAL ANALYSIS PLAN, Final Version 1.0
Protocol Number: ARQ-151-313	Sponsor: Arcutis Biotherapeutics, Inc.

roflumilast cream during the OLE study) to 7 (subjects in Cohort-Week 24 who completed the OLE) or 9 (subjects in Cohort-Week 52 who completed the OLE) vIGA-AD non-imputed values:

OLE Analysis Visit	Study/Analysis Visit
OLE Week -4	Parent study derived baseline value (refer to parent study Section 5.2)
OLE Week -3	Parent study / analysis visit Week 1
OLE Week -2	Parent study / analysis visit Week 2
OLE Day 1	Parent Study / analysis visit Week 4
OLE Week 4	OLE study / analysis visit Week 4
OLE Week 12	OLE study / analysis visit Week 12
OLE Week 24	OLE study / analysis visit Week 24
OLE Week 36*	OLE study / analysis visit Week 36
OLE Week 52*	OLE study / analysis visit Week 52

* Cohort-Week 52 subjects only.

Note: No missing data are expected for the OLE Week -4 to OLE Day 1 analysis visits since subjects must have completed a parent study to be eligible for enrollment in this OLE study.

Then, to comply with the definition of the parent studies' primary estimand (refer to parent studies Section 12.1.1), efficacy data assigned to a pre-specified analysis visit will be removed from the source data used for the multiple imputation process if subject's last dose day falls within the analysis visit window or is prior to the start of the analysis visit window used to assign data to a pre-specified analysis visit (refer to Section 12.2) for subjects who discontinued due to lack of efficacy or adverse event. This procedure will ensure that the data collected on or after intercurrent events are not used in the imputation process.

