13.1 Adverse Events

AEs will be coded according to the latest available version of MedDRA (Version 25.0 or higher).

A treatment emergent adverse event (TEAE) is defined as an AE that started post application of study medication at the Day 1 visit of study ARQ-151-313 or was present at treatment initiation but worsened during treatment, through study completion. See [Appendix 2](#) for handling of completely or partially missing dates for AEs. In the case where it is not possible to define an AE as treatment emergent or not, the AE will be classified as treatment emergent.

An overall summary of TEAEs will be presented by treatment group as defined in Section 5, which will include the total number of events, and the number and percentage of subjects who experienced at least one TEAE, TEAE by the maximum severity, TEAE by relationship and TEAE by the strongest relationship, treatment-emergent SAE, treatment-emergent Non-SAE, TEAE leading to study treatment discontinuation, TEAE leading to study discontinuation, TEAE on an application site, and TEAE leading to death. In addition, similar summary as described above will be presented by age group (refer to Section 6.6) for rollovers from study ARQ-151-311/312.

The number and percentage of subjects who experience at least one TEAE will be summarized by SOC, PT, and treatment group as defined in Section 5. A subject experiencing the same TEAE multiple times within the same PT will be counted only once for that PT. Similarly, a subject experiencing the same TEAE multiple time within the same SOC will be counted only once for

 Innovaderm Research	STATISTICAL ANALYSIS PLAN, Final Version 1.0
Protocol Number: ARQ-151-313	Sponsor: Arcutis Biotherapeutics, Inc.

that SOC. TEAEs will be sorted alphabetically by SOC and within each SOC, the PT will be presented by descending frequency. In addition, similar summary as described above will be presented by age group (refer to Section 6.6) for rollovers from study ARQ-151-311/312.

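### The vIGA-AD failure rule is triggered by leaving the study but dated from the last dose, so stopping only the cream for an AE is not a forced failure

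*SAP*

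**What the plan says.** **Failure rule.** SAP 5.5 defines both vIGA-AD secondary endpoints with one exception. It applies "for subjects who discontinued early from study due to an AE or lack of efficacy", and makes the subject a non-achiever at every analysis visit for which the day of last dose "falls within or is before the start of the analysis visit window".

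**Deletion rule.** SAP 6.2.1 removes efficacy data from the imputation source on the same last-dose timing, "for subjects who discontinued due to lack of efficacy or adverse event". The stated aim is: "This procedure will ensure that the data collected on or after intercurrent events are not used in the imputation process". The rule is said to follow the parent studies' primary estimand, which is defined in the parent SAPs.

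**Stopping treatment.** Protocol 4.7.5 opens with "A subject may discontinue study treatment for any of the following reasons". AEs are item 2 on that list, and there "the Investigator must follow the subject until the AE resolves or satisfactorily stabilizes". Protocol 5.9 also ends treatment for a confirmed, related Grade 3 laboratory abnormality and for a recurrent application-site reaction, the latter with follow-up until it resolves. Its bullet on SAEs and clinically significant AEs, however, speaks of discontinuation from the study.

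**Leaving the study.** Protocol 4.7.6 opens with "A subject may be removed from study participation for any of the following reasons" and gives seven reasons. None is an AE.

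**Reporting.** SAP 13.1 counts the two events separately: "TEAE leading to study treatment discontinuation, TEAE leading to study discontinuation".

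**The concern.** The rule's timing and its trigger point to different events. Dating failure from the last dose treats the end of treatment as the intercurrent event, but the trigger is exit from the study. SAP 5.5 itself lists the end-of-treatment date and the end-of-study date as separate items, so the two can differ.

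The protocol puts most AEs on the treatment side. A subject can therefore be off the cream for an AE without being coded as having left the study for that AE. This happens if the subject remains on study for a time, or later exits under another 4.7.6 reason such as own decision or interruption of more than half the doses. In either case the 5.5 exception does not apply.

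At stake is whether two subjects with the same AE and the same last dose are classified alike. For the one who is missed, the difference can only raise the reported long-term response.

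**Working it through.** The documents give no figure for how often this occurs, so there is nothing to reproduce. The check has three parts.

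**1. What the rule does as written.** The inputs are the SAP Table 3 windows: Week 4, Days 15–57; Week 12, 58–127; Week 24, 128–211; Week 36, 212–309; Week 52, Day 310 onward. A visit is a forced failure if the last dose lies inside or before its window. For a subject coded as leaving the study for an AE:

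- last dose Day 20: Weeks 4, 12, 24, 36 and 52
- last dose Day 100: Weeks 12, 24, 36 and 52
- last dose Day 140: Weeks 24, 36 and 52
- last dose Day 230: Weeks 36 and 52
- last dose Day 320: Week 52

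Cohort-Week 24 subjects have only the visits up to Week 24. For a subject with the same last dose who stops only the cream, no visit is a forced failure.

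**2. Whether an off-drug score can reach the analysis.** Protocol 5.6 collects vIGA-AD at unscheduled visits and waives it only when the visit is for reasons other than safety. SAP 5.4 uses an unscheduled or early-termination score when the window has no scheduled one. Take a last dose on Day 100 and an AE follow-up visit on Day 130. Day 130 lies in 128–211, so without a scheduled Week 24 score it becomes the Week 24 value. If it is 0 or 1, the subject is a Week 24 responder for the 0/1 endpoint; success also needs a 2-grade improvement. Coded as leaving the study for the AE, the same subject fails from Week 12 onward.

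The three planned vIGA-AD analyses then behave as follows:

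- *Multiple imputation, 6.2.1 read narrowly (study exit only):* the off-drug score is kept and counted.
- *Multiple imputation, 6.2.1 read broadly (treatment stops included):* the score is deleted and imputed. Because 5.5 does not force failure, an imputed 0 or 1 counts as response.
- *Non-responder imputation (6.2.2):* it acts on missing values only, so an observed off-drug score stands.
- *Observed cases (12.2.2):* an observed off-drug score stands.

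**3. Size, on assumptions that are not in the documents.** Overstatement = (share stopping the cream for an AE) × (share of those the rule misses) × (share of the missed counted as responders).

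- Low: 0.01 × 0.25 × 0.5 = 0.00125, or about 0.1 point.
- High: 0.03 × 0.75 × 0.5 = 0.01125, or about 1.1 points.

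A wider set takes 1–5% as stopping treatment only, all missed, with 30–70% of them scoring 0 or 1:

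- Low: 0.01 × 0.3 = 0.003, or 0.3 point.
- High: 0.05 × 0.7 = 0.035, or 3.5 points.

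For scale, with the planned 1500 subjects and 50% response (assumed), the 95% half-width is 1.96 × √(0.5 × 0.5 / 1500) = 0.025, or 2.5 points. It is wider within a treatment group, and at Weeks 36 and 52, where Cohort-Week 24 contributes no data.

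**The case against.** A reader might infer that anyone taken off the cream for an AE simply goes on counting as a responder. The documents do not support that. Without the exception, SAP 5.5 classifies by the actual score: 2 or more is non-response, and success also needs the 2-grade improvement.

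The other side has further points:

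- No section provides scheduled efficacy visits after a treatment-only stop. The follow-up wording concerns AEs, and Protocol 5.7.4 limits it to about a month. This narrows the route but does not close it, because an AE follow-up visit or an early-termination visit can still supply a score.
- The 5.9 bullet does foresee AE-driven exit from the study, which is the 5.5 trigger. This stands for subjects so coded. It does not reach the treatment-only stops in the same section.
- A broad reading of 6.2.1 would keep off-drug scores out of the imputation, so its stated aim could be met. This also stands, but the deleted value is then imputed rather than set to failure.
- After an exit coded to another reason, later missing visits are failures under non-responder imputation. This is correct; only observed off-drug scores survive there.
- The parent-study estimand is not in these documents, so whether a treatment-only stop was an intercurrent event there cannot be checked. This stands, and the fix must allow for it.

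**Conclusion.** The mismatch is real. SAP 5.5 and 6.2.1 word their triggers differently, and neither states that an AE-related permanent stop of treatment alone is a failure. None of the three planned vIGA-AD analyses corrects this fully. For a missed subject's own classification, the effect can only favour response.

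A reader might go further and conclude that long-term response is known to be overstated. The documents do not show that: the number of such subjects, their coding and their scores are all unknown. On the first set of assumptions the effect is about 0.1 to 1.1 points. The wider set reaches 3.5 points, but only if 5% stop treatment alone, all are missed and 70% of them score 0 or 1. A small effect is the more likely outcome.

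The endpoint is secondary and descriptive in a single-arm safety study without hypothesis tests (SAP 5.7), so no error rate or sample size is affected. The case for the change is consistency at little cost.

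**What to change.** Define the intercurrent event once: permanent discontinuation of study treatment or of the study due to an AE or lack of efficacy, dated from the last dose. Use that wording in both vIGA-AD bullets of SAP 5.5 and in 6.2.1. First check it against the parent-study estimand that 6.2.1 cites; if that estimand treats treatment-only stops differently, say so and state how off-treatment scores are handled.

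For AEs, use the data on TEAEs leading to treatment discontinuation that SAP 13.1 already needs. Confirm whether a lack-of-efficacy reason for stopping treatment is captured, since Protocol 4.7.5 does not list one.

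The wording on treatment stops and study exit in Protocol 4.7.5, 4.7.6 and 5.9 should be reconciled. No clinical rule is proposed here.

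The cost is SAP wording and that one check of the data collected. Response rates may come out slightly lower. Because the rule covers the whole window containing the last dose, some scores taken before the stop will also become failures, as already happens for subjects who leave the study.

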- Cumulative time (days) on BIW dosing: Subjects may have more than 1 BIW dosing interval. The duration of succeeding BIW dosing intervals will be derived in a manner similar to the first and durations will be summed across all intervals for a subject. This endpoint will be calculated only for subjects who enter the post-OLE Week 4 study period with at least one BIW dosing interval.
- Percent of time on BIW dosing: The cumulative time (days) on BIW dosing will be divided by the Post-OLE Week 4 study duration and multiplied by 100 to measure the percentage of study days on BIW dosing. This endpoint will be calculated only for subjects who enter the post-OLE Week 4 study period with at least one BIW dosing interval.
- Duration (days) of first disease control will be calculated from the first disease control to the time subjects revert to a QD dosing or have a vIGA-AD score ≥ 2 , whichever comes first. Disease control is defined as achievement of a vIGA-AD score of 0, a switch to BIW dosing, and maintenance of a vIGA-AD score of 0 or 1. Disease control starts with the later date of a vIGA-AD score of Clear (0) on or after OLE Week 4 and the switch to BIW dosing. Subject's last contact date will be used to censor this endpoint (time-to-event analysis) or as the end date of this duration (analyzed as a continuous endpoint) for subjects who never lose disease control after the start of the first disease control interval. This endpoint will be calculated only for subjects who enter the post-OLE Week 4 study period and had at least one disease control interval.
- Cumulative time (days) with disease control. Subjects can come in and out of disease control. The duration for each interval will be derived as described above for the first interval. Cumulative time with disease control will sum the durations for all intervals where disease was under control as defined in the previous bullet. This endpoint will be calculated only for subjects who enter the post-OLE Week 4 study period and had at least one disease control interval.
- Percent of time with disease control. The cumulative time with disease control will be divided by the Post-OLE Week 4 study duration and multiplied by 100 to express cumulative time as a percentage of the duration of time that each subject spent in the study after OLE Week 4. This endpoint will be calculated only for subjects who enter the post-OLE Week 4 study period and had at least one disease control interval.

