 Innovaderm Research ■■■	STATISTICAL ANALYSIS PLAN, Final Version 1.0
Protocol Number: ARQ-151-313	Sponsor: Arcutis Biotherapeutics, Inc.

- Duration (days) of the first vIGA-AD of Clear (0) will be calculated from the first vIGA-AD score of 0 during the study to the next vIGA-AD score > 0. Subject's last contact date will be used to censor this endpoint (time-to-event analysis) or as the end date of this duration (analyzed as a continuous endpoint) for subjects who never revert to a vIGA-AD score > 0. This endpoint will be calculated only for subjects who had at least one vIGA-AD score of Clear (0) interval.
- Cumulative time (days) with vIGA-AD of Clear (0). Subjects can have more than 1 vIGA-AD of Clear (0) interval. The duration for each interval will be derived as described above for the first interval. Cumulative time with vIGA-AD of 0 will sum the durations for all intervals. This endpoint will be calculated only for subjects who had at least one vIGA-AD score of Clear (0) interval.
- Percent of time with vIGA-AD of Clear (0). The cumulative time will be divided by the study duration and multiplied by 100 to express cumulative time as a percentage of the duration of time that each subject spent in the study. This endpoint will be calculated only for subjects who had at least one vIGA-AD score of Clear (0) interval.
- Duration (days) of the first vIGA-AD of Clear (0) or Almost Clear (1) will be calculated from the first vIGA-AD score of 0 or 1 during the study to the next vIGA-AD score > 1. Subject's last contact date will be used to censor this endpoint (time-to-event analysis) or as the end date of this duration (analyzed as a continuous endpoint) for subjects who never revert to a vIGA-AD score > 1. This endpoint will be calculated only for subjects who had at least one VIGA-AD with a score of Clear (0) or Almost Clear (1) interval.
- Cumulative time (days) with vIGA-AD of Clear (0) or Almost Clear (1). Duration with vIGA-AD score of 0 or 1 measures the duration for the first interval with a VIGA-AD score of 0 or 1. There can be more than 1 interval. Cumulative time with vIGA-AD of 0 or 1 will sum the durations for all intervals. The duration for each interval will be derived as described above for the first interval. This endpoint will be calculated only for subjects who had at least one VIGA-AD with a score of Clear (0) or Almost Clear (1) interval.

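### Time on twice-weekly dosing runs past the last dose to the date of last contact, and open disease-control and clear intervals can run past the last vIGA-AD

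*SAP*

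**What the plan says.** SAP 5.5 gives each interval endpoint its own closing event.

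- **BIW dosing:** the first interval "will be calculated from the first BIW dosing to the start of the succeeding QD dosing interval".
- **Disease control:** from the start of control "to the time subjects revert to a QD dosing or have a vIGA-AD score" of 2 or more, whichever is first.
- **Clear:** the first interval "will be calculated from the first vIGA-AD score of 0 during the study to the next vIGA-AD score > 0". Clear or almost clear works the same way, with a score above 1 as the closing event.

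If no closing event is recorded, the subject's "last contact date will be used to censor this endpoint (time-to-event analysis) or as the end date of this duration". For BIW dosing, last contact serves as the censoring date "or as the end date of this duration (analyzed as a continuous endpoint) for subjects who do not revert to a QD dosing regimen". Last contact is itself a maximum: "Date of last contact = the latest of last study visit date, last dose date, end-of-study date and end-of-treatment date". Cumulative and percent-of-time endpoints sum the same intervals. The percent-of-time denominator for BIW dosing and disease control also ends at last contact.

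SAP 11 reuses the 5.5 cumulative and percent time for its maintenance-dosing summary, but counts days on OLE treatment only to the last treatment date. SAP 12.3.1 reports durations as means with 95% CIs and by Kaplan-Meier, with reasons for censoring. SAP 12.3.2 plans no sensitivity analysis for these endpoints.

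**The concern.** No rule ends an interval when the cream is stopped for good, or at the last vIGA-AD. Protocol 4.7.5 (stopping treatment) is separate from 4.7.6 (leaving the study), so a subject can be off drug and still in contact. After an adverse event "the Investigator must follow the subject until the AE resolves or satisfactorily stabilizes", and Protocol 5.1.12 allows follow-up for up to 30 days after end of treatment. Last contact can therefore fall well after the last dose, and the days between are labelled as time on BIW dosing.

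The vIGA-AD-based intervals have a related problem. The phone visits at Weeks 18, 30 and 44 collect no vIGA-AD. If one of them is the last contact, the interval extends over weeks in which skin status was not assessed.

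SAP 6.6 uses the BIW and disease-control endpoints to examine long-term maintenance of effect. At stake are the reported durability of response and the reported exposure to maintenance dosing.

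**Working it through.** The plan states no figure on this point, so there is none to reproduce. The steps below apply its date rules.

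**Inputs.** Visit day = 7 x week + 1 (SAP 5.4 target days): Week 4 = 29, Week 12 = 85, Week 24 = 169, Week 36 = 253. The same formula puts the phone visits at Day 127 (Week 18), 211 (Week 30) and 309 (Week 44). Open intervals are counted as end - start + 1, the convention 5.5 states for the post-Week 4 duration. Lag (last dose or last vIGA-AD to last contact) and the share of subjects stopping with an open interval are not in the documents and are assumed.

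**1. BIW days.** BIW from Day 29, last dose Day 85, no return to QD, last contact Day 115 (30-day lag).

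- SAP rule: 115 - 29 + 1 = 87
- To last dose: 85 - 29 + 1 = 57, so the SAP figure is 87/57 = 1.53 times as large (+53%)
- Days on treatment (SAP 11): 85 - 1 + 1 = 85

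BIW time (87) exceeds total treatment time (85). For lags of 7, 60 and 90 days the rule gives 64, 117 and 147 days, still against 57.

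**2. Phone visit as last contact.** This takes a phone visit to count as a study visit. Gap from the last scheduled vIGA-AD:

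- Week 12 to 18: 127 - 85 = 42 days
- Week 24 to 30: 211 - 169 = 42 days
- Week 36 to 44: 309 - 253 = 56 days

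A subject clear at Weeks 4 and 12, reached by phone at Week 18 and then lost is credited with at least 127 - 29 + 1 = 99 clear days, against 85 - 29 + 1 = 57 to the last vIGA-AD.

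**3. Percent of time on BIW.** Numerator and denominator share the end date.

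| Course (denominator starts Day 29) | SAP rule | Both ended at last dose |
|---|---|---|
| BIW Day 29 to last dose Day 85, contact Day 115 | 87/87 = 100% | 57/57 = 100% |
| QD to Day 84, BIW Days 85-113, contact Day 143 | 59/115 = 51% | 29/85 = 34% |
| BIW from Day 29, QD from Day 85, last dose Day 113, contact Day 143 | 56/115 = 49% | 56/85 = 66% |

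The percentage can be unchanged, too high or too low.

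**4. Mean duration.** The rise is (share with an open interval at stop) x (lag): 5% x 7 = 0.4 day; 20% x 30 = 6 days; 30% x 60 = 18 days.

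**5. Kaplan-Meier median.** Simulation with exponential loss of control, 336 days of follow-up and 200,000 subjects per setting. Medians in days, by lag after the true stop:

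| True median | Dropout | Lag 0 | Lag 30 | Lag 60 |
|---|---|---|---|---|
| 200 | 10% | 199.4 | 201.1 (+0.9%) | 202.8 (+1.7%) |
| 200 | 30% | 199.7 | 206.1 (+3.2%) | 212.1 (+6.2%) |
| 100 | 30% | 100.3 | 103.4 (+3.1%) | 105.9 (+5.6%) |

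**The case against.** Several points on the other side stand.

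- **Late contact is often observed contact.** An early termination visit repeats the Week 52 procedures (Protocol 5.5), and unscheduled visits for safety collect vIGA-AD (Protocol 5.6). If Day 115 in step 1 is such a visit, a score of 2 or more closes disease control and a score above 0 closes clear. If the subject is still clear, that is an observation. Step 1 therefore concerns BIW time only. No vIGA-AD result closes a BIW interval by itself.
- **A reader might infer that the rule always favours the drug.** It does not. The third row of step 3 shows percent of time falling under the SAP rule.
- **A reader might infer that lost subjects are credited with long unobserved response.** "A subject will be considered lost to follow-up after three phone and three email attempts" and a certified letter, so closure may come late. But the documents do not say how the end-of-study date is recorded for a lost subject, so no lag can be fixed. Backdating to the last visit would shrink the excess without removing the phone-visit gap.
- **A reader might infer a contradiction with the responder endpoints,** which SAP 5.5 scores as failures after discontinuation for AE or lack of efficacy. That exception is written for the by-visit vIGA-AD endpoints. Handling the same event differently for a duration endpoint is an estimand choice. Worsening on BIW also leads to resumed QD dosing under Protocol 4.1, which already closes the interval.

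The endpoints are classed as other efficacy, no hypothesis is tested, and censoring reasons are tabulated. That lowers the stakes, but listing reasons does not correct the end date.

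**Conclusion.** The point holds for BIW time without further assumption: if the subject stops while on BIW and any later date enters last contact, off-drug days are reported as time on BIW dosing, and SAP 11 can show more BIW days than treatment days. For disease control and clear or almost clear, it holds when the last contact brings no vIGA-AD.

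Durations and cumulative times for open intervals can only be overstated. One subject's figure can be far off (+53% at a 30-day lag, which the protocol's follow-up period allows). The effect on group means is 0.4 to 18 days over the assumed range, and Kaplan-Meier medians rise by about 1-6%. Percent of time has no fixed direction. The actual size in this trial cannot be derived, because lag and dropout are not given.

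**What to change.** In SAP 5.5:

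1. End or censor open BIW intervals at the last dose date, and use that date as the end of the percent-of-time-on-BIW denominator. SAP 11 then follows.
2. Censor disease-control, clear and clear/almost-clear intervals with no recorded closing event at the last vIGA-AD assessment, including early termination and unscheduled visits, with matching denominators. Define the study duration used for the clear endpoints, which 5.5 leaves undefined.
3. Keep any vIGA-AD worsening observed after the last dose as a closing event. Cutting at treatment end would erase real relapses: a subject clear at Day 85, last dose Day 100, scored 3 at an early termination visit on Day 107 would be censored as clear.
4. Optionally, treat discontinuation for AE or lack of efficacy as loss of control, as a sensitivity analysis only.

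The cost is SAP wording and minor reprogramming, using dates the study already collects. Reported durations become slightly shorter for subjects who stop early. An interval opened by the last available vIGA-AD shrinks to a day or less, so the SAP should state how it is counted.
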